12.3 Estimation of Sample Size

In the Phase 2a trial, IGA response rates of 21.6% and 11.8% were observed for DS107 and Placebo respectively. Assuming these rates and a significance of 5%, 300 evaluable patients (100 patients per treatment arm) will yield 45% power for comparisons between the active doses and placebo in this study.

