2.2.6 Methods for Handling Missing Data

PROC GENMOD will be used to account for any missing data and early withdrawal for FAS.

The GENMOD procedure will estimate the working correlation from data containing both types of missing values by using the *all available pairs* method, in which all non-missing pairs of data are used in the moment estimators of the working correlation parameters. The resulting covariances and standard errors are valid under the missing completely at random (MCAR) assumption.

A sensitivity analysis will be performed for the Week 8/Exit outcome under the missing at not random (MNAR) assumption for the primary efficacy analyses using the FAS. An extreme analysis will be used to identify the possible outcome considering two scenarios: An extreme analysis will be used to identify the possible outcome considering the worst case for both active treatments and best case for vehicle (Scenario 1) and then the reverse (Scenario 2). If any extreme cases result in statistical significance, then the maximum degree of relaxation per

treatment group still reaching statistical significance will be displayed for each scenario. A two-sided Fisher Exact Test will be utilized for these analyses.

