2.2.8 Statistical Hypotheses

The overall null hypothesis (H_0) for each analysis is the equality of the means for the three treatment groups. A global test will be performed across all three treatment groups to allow for a penalty-free comparison of the comparison of the 1g and 2g concentrations against the placebo control. In the event of a global difference (two-sided $p < 0.05$), then the between-treatment comparison of the 2g active treatment group to placebo is performed. If significant (two-sided $p < 0.05$) then the between-treatment comparison of the 1 g active treatment group to the placebo is performed; otherwise the p-values will be regarded as descriptive statistics. The Type I error rate is controlled for by the hierarchical approach. All testing will be two-sided; global tests will be performed at the 0.05 level. Testing between the 2 active groups will be considered descriptive statistics.

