2.2.12.1 Primary Endpoint

The primary efficacy variable will be the proportion of patients achieving an IGA score of 0 (clear) or 1 (almost clear) and a decrease of at least 2 points in IGA from baseline to week 8. This is a binary endpoint.

The primary endpoint will be analyzed using a Generalised Linear Model (PROC GENMOD) with treatment arm, moderate/severe AD, baseline IGA value, visit and DS treatment dose as factors. The primary analysis will be based on the FAS and repeated for the PPS as a supportive analysis.

This analysis will be performed using SAS PROC GENMOD with code similar to the following:

```
proc genmod data=subjresults descending;  
  class trt visit subj AD;  
  model outcome=trt visit trt*visit AD B_IGA /dist=bin;  
  repeated subject=subj/corr=unstr;  
  slice trt*visit / sliceby=visit ilink cl diff;  
run;
```

where fas= Full Analysis Set (FAS), outcome= patients in each treatment arm at week 8 who achieve an IGA score of 0 (clear) or 1 (almost clear) and a decrease of at least 2 points in IGA from baseline. B_IGA is the baseline IGA value.. The dist=bin option of the model statement specifies that the logit transformation will be applied to outcome prior to analysis. The cl option specifies that two-sided 95% confidence intervals will be provided and the ilink option specifies the transformation from the logit scale to the probability scale. The between-treatment effects are determined from the diff option of the slice statement. Results will be presented separately for moderate and severe AD for both the FAS and PPS populations. The model will be used to estimate Week 8 effect.

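### The SAP's only MNAR check on the primary endpoint changes the test along with the missing-data assumption, and its display rule does not lead from a failed worst case to the tipping point

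*SAP*

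**What the plan says.** SAP 2.2.6 plans one missing-not-at-random check on the Week 8 primary endpoint in the FAS. It takes "the worst case for both active treatments and best case for vehicle (Scenario 1) and then the reverse (Scenario 2"); vehicle here must mean placebo. The filled tables are tested as follows: "A two-sided Fisher Exact Test will be utilized for these analyses". A further display is conditional: "If any extreme cases result in statistical significance, then the maximum degree of relaxation per" treatment group is shown for each scenario, limited to settings that remain significant. The section does not say whether Fisher is pairwise or three-arm, whether the global test applies first, or which direction of effect counts.

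The primary analysis in SAP 2.2.12.1 is different in kind. It is a binomial GENMOD model with repeated visits, specified "with treatment arm, moderate/severe AD, baseline IGA value, visit and DS treatment dose as factors", and coded as "model outcome=trt visit trt*visit AD B_IGA /dist=bin". SAP 2.2.12 asks for the severity covariate in all primary and secondary efficacy models. SAP 2.2.8 adds: "All testing will be two-sided; global tests will be performed at the 0.05 level". It requires a significant global test, then 2g v placebo, then 1g v placebo.

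Protocol 12.9.2 planned a different sensitivity analysis, jump to reference with placebo as the reference. It does not appear in the SAP, so the extreme-case check is the SAP's only departure from its missing-data assumption for this endpoint.

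**The concern.** A sensitivity analysis should hold everything fixed except the assumption under examination. This one changes two things together: how missing outcomes are treated, and the test applied to the result. Fisher's exact test is conservative at these rates and ignores severity. If significance is lost, a reader cannot tell how much is due to the missing data.

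The second weakness is the display rule. A tipping-point analysis is useful because it shows how unfavourable the missing outcomes must be before the conclusion changes. The written rule reports only what can be relaxed while significance holds. When Scenario 1 fails, it does not define the steps from that worst case to the point where significance returns.

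At stake is how readily the check can be interpreted. The validity of the primary result is not in question here.

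**Working it through.** **Inputs.** 100 per arm, 21.6% v 11.8%, and 45% power (Protocol 12.3). Placebo 10% plus 15 points, so 25% v 10%, at 100 per arm (SAP 2.2.9). Two-sided 0.05 with a global test first (SAP 2.2.8). The documents give no dropout rate, so every missing count below is an assumption, taken as equal across arms.

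**1. The plan's own figures.** Power = Φ{[|p1−p0|√n − 1.96√(2p̄q̄)] / √(p1q1+p0q0)}.

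At 21.6% v 11.8%, p̄ = 0.167: (0.980 − 1.034)/0.523 = −0.103, giving 45.9% against the stated 45%.

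For 25% v 10% at 80% power (the power named in SAP 2.2.10; 2.2.9 states none): (1.053 + 0.443)²/0.15² = 99.5, so 100 per arm. Both reproduce.

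**2. Effect of the test alone.** With no missing data, both scenarios equal the observed data. Without covariates, the primary Week 8 contrast then reduces to a Wald test of the log odds ratio, z = ln(OR)/√(1/a + 1/(n−a) + 1/c + 1/(n−c)).

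Example: 2g 22/100, 1g 11/100, placebo 11/100. The global Wald test gives p = 0.0445. For 2g v placebo, ln[(22×89)/(11×78)] = 0.825, SE 0.4005, z = 2.06, Wald p = 0.039. Fisher gives p = 0.056.

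Summing binomial probabilities over all 100 v 100 tables:

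| Rates | Wald wins | Fisher wins | Wald wins that Fisher loses |
|---|---|---|---|
| 25% v 10% | 80.4% | 76.2% | 5.2% |
| 21.6% v 11.8% | 44.9% | 39.5% | 12.1% |

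Fisher's actual two-sided size is 2.9% with both arms at 10% and 3.1% with both at 11.8%.

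Requiring the global test first (20,000 simulated trials per setting, unadjusted) gives a smaller share of 2g wins lost:

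| 2g / 1g / placebo | 2g wins | Lost under Fisher |
|---|---|---|
| 25 / 25 / 10% | 74.4% | 2.8% |
| 25 / 17.5 / 10% | 69.3% | 1.0% |
| 21.6 / 21.6 / 11.8% | 34.4% | 4.0% |

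With severity adjustment but no global gate, simulation gives 7% and 15% in place of 5% and 12%. It assumes 35% severe and a severity odds ratio of 0.35. Phase 2a (Protocol 1.6) is close to both: (22+13)/102 = 34% severe or very severe, and odds ratio (3/32)/(14/53) = 0.35.

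**3. Scenario 1 at observed rates of 25% v 10%** (counts rounded):

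| Missing per arm | Filled DS107 v placebo | Fisher p | Wald p |
|---|---|---|---|
| 0 | 25 v 10 | 0.0085 | 0.0067 |
| 2 | 24 v 12 | 0.042 | 0.030 |
| 3 | 24 v 13 | 0.068 | 0.048 |
| 4 | 24 v 14 | 0.104 | 0.074 |
| 10 | 22 v 19 | 0.73 | 0.60 |

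Matching the test moves the break point by one patient per arm, from 3 to 4. Over all tables with 10 missing per arm, Scenario 1 under Fisher keeps about 5% of wins at 25/10 and about 1% at 21.6/11.8.

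**4. Scenario 2 and the trigger.** In the same cases Scenario 2 gives 27 v 10 (3 missing, p = 0.003) and 32 v 9 (10 missing, p < 0.001). With 1, 2, 3, 5 or 10 missing per arm, enumeration finds it Fisher-significant in effectively every trial with a significant primary result. The trigger will normally fire.

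**5. Direction.** Scenario 1 becomes significant in favour of placebo at 25 missing per arm at 25/10 (19 v 33, p = 0.036; with the half-count rounded down, 19 v 32, p = 0.051). At 21.6/11.8 this happens at 21 per arm (17 v 30, p = 0.045). If the arms have equal rates it happens at 11-12 per arm (9 v 20, p = 0.043; 10 v 22, p = 0.033), and by symmetry Scenario 2 is then significant for DS107. The rule treats all of these as significance.

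**The case against.** The strongest reply has four parts.

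- **Overturning the primary result.** A reader might infer that the check can overturn a sound result with nobody missing. The documents do not support that. No rule in SAP 2.2.6, 2.2.8 or 2.2.12.1 gives the check such force, and with no missing data it has no question to answer. Disagreement means only that two p-values fall on either side of 0.05, and it needs a borderline result. This part stands.
- **Withholding the relaxation display.** A reader might also infer that the display will usually be missing, so that the check says nothing about robustness. That is too strong. Any significant extreme triggers it, and Scenario 2 normally is significant after a positive primary result. What remains is that the display covers only settings that stay significant and does not map the way back from a failed Scenario 1.
- **Blaming Fisher for Scenario 1 or for a placebo win.** Neither holds. Scenario 1 is severe under any test. At 19 v 33 the Wald test is also significant (p = 0.025), and at 17 v 29 Wald is significant (0.046) while Fisher is not (0.064). Two-sided testing is the SAP's general convention, and the counts show the direction. Stating it is still a useful clarification.
- **Practicality of refitting.** The primary model spans several visits and could fail in sparse strata; Phase 2a had 0/13 placebo responders in severe or very severe disease. Fisher always computes. This is fair, and the fix needs a fallback.

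**Conclusion.** The point holds as a matter of interpretability. The check replaces the adjusted primary model with an unadjusted Fisher test, so a lost p-value cannot be attributed to missing data alone. The test by itself accounts for 5-12% of pairwise unadjusted wins, and about 1-4% of 2g wins after the global gate. These figures assume 100 per arm, the documents' planning rates, no missing data, and a Wald test standing in for the primary contrast.

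The display rule is incomplete: it omits direction and the route from a failed Scenario 1 to the tipping point. Scenario 1 failing at 3-4 missing per arm, and a placebo-favouring result at 21-25 per arm at the planning rates, depend on assumed missing counts and are not defects of Fisher. The change is worth making because it is cheap and this is the SAP's only MNAR analysis of the primary endpoint.

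**What to change.** Amend SAP 2.2.6 as follows.

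1. After filling missing Week 8 outcomes, refit the primary GENMOD model with the same covariates, leave earlier visits as observed, and read off the Week 8 contrast for each dose against placebo. With nobody missing, the sensitivity result then equals the primary result.
2. Name a fallback for a stratum too sparse to fit, such as a severity-stratified exact test.
3. Always show the full tipping-point grid for each dose: missing DS107 patients counted as responders by missing placebo patients counted as responders. Scenarios 1 and 2 are two corners of it.
4. State the direction of effect in every cell, and count the primary result as retained only where the effect favours DS107.
5. Remove the trigger that makes the display conditional on a significant extreme.

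The cost is SAP wording and one looped analysis, with no new data. With 10 missing per arm, for example, the grid has 11 × 11 = 121 cells per dose.

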2.2.7 Safety Monitoring

No safety monitoring committees are planned for the study.

2.2.8 Statistical Hypotheses

The overall null hypothesis (H_0) for each analysis is the equality of the means for the three treatment groups. A global test will be performed across all three treatment groups to allow for a penalty-free comparison of the comparison of the 1g and 2g concentrations against the placebo control. In the event of a global difference (two-sided $p < 0.05$), then the between-treatment comparison of the 2g active treatment group to placebo is performed. If significant (two-sided $p < 0.05$) then the between-treatment comparison of the 1 g active treatment group to the placebo is performed; otherwise the p-values will be regarded as descriptive statistics. The Type I error rate is controlled for by the hierarchical approach. All testing will be two-sided; global tests will be performed at the 0.05 level. Testing between the 2 active groups will be considered descriptive statistics.

2.2.9 Sample Size Justification

The sample size for the topical DS107 Phase IIb study was informed from the post-hoc analysis of the IGA responder data which will be used as the primary endpoint. The positive efficacy data over 4 weeks showed no sign of a plateau and suggests further improvements may be observed at week 8. The sample size was estimated following extrapolation of the IGA responder rate data of the Phase IIa results at weeks 2, 3 and 4 to week 8. Assuming a placebo response rate of 10%, 100 patients per treatment arm (300 patients in total) will be required to detect an absolute difference of 15% in the response rate between an active dose and placebo.

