Overall, DS107 capsules administered to 48 healthy volunteers as a single 500mg, 1g, 2g, or 4g dose under fasted conditions; as a single 1g dose under fed conditions; and as multiple 2g and 4g doses taken once daily for 28 consecutive days was well tolerated.

DS107 Capsules Phase 2a Study

This 8 week study was a randomized, placebo-controlled, double-blind, multi-centre Phase 2a trial to investigate the efficacy, safety, tolerability and bioavailability of 2g DS107 administered orally once daily versus 2g placebo administered orally once daily in adult patients with moderate to severe AD. The primary efficacy endpoint was defined as the proportion of patients achieving an Investigator Global Assessment (IGA) of 0 (clear) or 1 (almost clear) and a decrease of at least two points in IGA at Week 8. Secondary efficacy variables included IGA measurements, pruritus (obtained from the Scoring of Atopic Dermatitis [SCORAD] visual analog scale [VAS]), Eczema Area and Severity Index [EASI], body surface area (BSA), Patient-Oriented Eczema Measure (POEM), Dermatology Life Quality Index (DLQI) and SCORAD.

There was a trend toward a statistically significant higher number of patients who achieved an IGA score of 0 or 1 and a 2 point drop in the DS107 capsules group at Week 8 in comparison to Placebo: 11 (21.6%) Responders in the DS107 capsules group, and 6 (11.8%) in the Placebo group (p-value: 0.057). A similar trend was also observed in the number of patients achieving a decrease of at least 2 points in the IGA score at Week 8 with 14 (27.5%) in the DS107 capsules group and 8 (15.7%) in the Placebo group (p-value: 0.065).

Further analysis was performed on the severity groups (Moderate and Severe/Very Severe at baseline) comparing the DS107 capsules group to the Placebo group in terms of Responders, using the CMH test stratified for Site. The proportion of Responders was always greater in the DS107 capsules group compared to the Placebo group in both the moderate and the severe/very severe populations.

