Topical administration of DS107 cream at dose strengths of 0.1%, 0.5%, 1%, 2.5% and 5% (up to 30 mg topical DGLA/day) had no clinically significant effect on any of the following parameters; vital signs, ECG or laboratory safety parameters; haematology, biochemistry, urinalysis. No serious or non-serious expected or unexpected adverse events related to the IMP were observed. There were no clinically significant abnormalities or changes from baseline values in the local tolerability assessments. There were no clinically significant abnormalities or changes from baseline values in the local tolerability assessments. All patients completed study procedures as per protocol and there were no significant protocol deviations affecting the safe conduct of the study.

Two Phase 2 proof-of-concept studies were completed with DS107 cream: Study DS107E-02 in patients affected by mild to moderate AD, and Study DS107E-03 in patients with mild to moderate acne vulgaris.

Study DS107E-02 was a randomized, double-blind, placebo-controlled Phase 2 study to assess the efficacy and safety of topically applied DS107 cream in patients with mild to moderate AD. Four parallel groups of patients with confirmed AD were investigated in this study to compare three different doses of DS107 cream (0.1%, 1%, and 5%) with placebo over a 28-day treatment period. During the 28 days of treatment, patients liberally applied their assigned treatment to all affected or commonly affected areas twice daily (morning and evening).

DS107 Cream treatment groups in Study DS107E-02 were similar to the Vehicle group for number of adverse events, event severity and seriousness. No deaths or SAEs occurred during the study. Except for CPK, no large treatment differences were seen in any of the laboratory parameter mean values. The mean values of the vital sign parameters were largely stable across treatment groups. Overall, DS107 cream was well tolerated, with a safety profile similar to the vehicle cream.

Study DS107E-03 was a Phase 2 proof-of-concept study in patients with mild to moderate acne vulgaris carried out as a double-blind, randomised study with two active treatment groups of 1% and 5% DS107 and a vehicle group. The study consisted of a washout period (maximum 14 days); a 12-week treatment period and a 4-week follow-up period. During the 12 weeks of treatment, patients applied the assigned treatment to all affected areas of skin twice daily (morning and evening).

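### SAP 2.2.9 justifies 100 per arm with a 15-point difference for a topical study; protocol 12.3 supports the same number with the oral Week 8 rates and 45% power

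*SAP*

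**What the plan says.** SAP 2.2.9 (Sample Size Justification) begins: "The sample size for the topical DS107 Phase IIb study was informed from the post-hoc analysis of the IGA responder data". It continues: "The positive efficacy data over 4 weeks showed no sign of a plateau". The planning effect comes from "extrapolation of the IGA responder rate data of the Phase IIa results at weeks 2, 3 and 4 to week 8". With 10% assumed on placebo, it says that 100 patients per arm "will be required to detect an absolute difference of 15% in the response rate between an active dose and placebo". The section gives no power. The significance level is set just before it, in SAP 2.2.8, at two-sided 0.05.

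Protocol 12.3 (Estimation of Sample Size) takes the Phase 2a response rates of 21.6% and 11.8% at 5% significance and concludes: "300 evaluable patients (100 patients per treatment arm) will yield 45% power for comparisons between the active doses and placebo in this study".

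Protocol 1.6 gives the origin of those rates. The oral Phase 2a study lasted 8 weeks and compared "2g DS107 administered orally once daily versus 2g placebo administered orally once daily in adult patients". At Week 8 it recorded "11 (21.6%) Responders in the DS107 capsules group, and 6 (11.8%) in the Placebo group". The only 4-week efficacy study in atopic dermatitis that protocol 1.6 describes is a cream study, which compared "three different doses of DS107 cream (0.1%, 1%, and 5%) with placebo over a 28-day treatment period".

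**The concern.** One sample size has two justifications that cannot both describe this trial. The SAP names a topical study, but every arm here takes capsules by mouth. It extrapolates from Week 4, but the oral Phase 2a study had already observed the endpoint at Week 8. It uses a difference of 15 points, where the protocol uses the observed 9.8. The extrapolated rates appear in neither document, so the 15 points cannot be traced.

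At stake is what the trial can claim about its planned size. On the protocol's figures, 300 patients give slightly less than an even chance of detecting the effect seen in Phase 2a. On the SAP's figures, the same 300 correspond to about 80% power. Someone who cites either document for the design would describe a different trial.

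**Working it through.** **Inputs.**
- SAP: placebo 10% and a 15-point difference, so 25% on active; 100 per arm (SAP 2.2.9); two-sided 0.05 (SAP 2.2.8).
- Protocol: 11.8% and 21.6%, 100 per arm, 5%, stated power 45% (protocol 12.3); tests two-sided (protocol synopsis).
- Phase 2a counts at Week 8: 11/51 = 21.6% and 6/51 = 11.8% (protocol 1.6).

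**Formula.** Pooled-variance comparison of two proportions, single dose against placebo. With p̄ the mean of p₀ and p₁, and d = p₁ − p₀:

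- s₀ = √[2p̄(1−p̄)] and s₁ = √[p₀(1−p₀) + p₁(1−p₁)]
- power = Φ[(d√n − 1.96·s₀)/s₁]
- n per arm for 80% power = [(1.96·s₀ + 0.8416·s₁)/d]²

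**Protocol figure.** p̄ = 0.167, s₀ = 0.5275, s₁ = 0.5229, d = 0.098.
- Power = Φ[(0.980 − 1.0338)/0.5229] = Φ(−0.103) = 45.9%. The stated 45% reproduces.
- n for 80% = 226.2, so 227 per arm.

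**SAP figure.** p̄ = 0.175, s₀ = 0.5374, s₁ = 0.5268, d = 0.150.
- Power = Φ[(1.500 − 1.0532)/0.5268] = Φ(0.848) = 80.2%.
- n for 80% = 99.5, so 100 per arm. The SAP's 100 reproduces if 80% was the intended power.

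**Which input drives the gap?** Exchange the placebo rates and keep the differences:

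| Placebo | Difference | Power at 100 per arm | n per arm for 80% |
|---|---|---|---|
| 10% (SAP) | 15 points (SAP) | 80.2% | 100 |
| 11.8% (protocol) | 15 points (SAP) | 77.1% | 108 |
| 10% (SAP) | 9.8 points (protocol) | 49.4% | 207 |
| 11.8% (protocol) | 9.8 points (protocol) | 45.9% | 227 |

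The assumed difference explains nearly all of it.

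**Choice of test.** By exact enumeration, Pearson chi-square gives 81.6% and 46.8%, and Fisher's exact test 76.2% and 39.5%, for the SAP and protocol inputs respectively. The gap remains under either test.

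**Testing sequence.** The figures above are for one comparison. SAP 2.2.8 tests all three arms globally, then 2g against placebo, then 1g against placebo, each at two-sided 0.05. Simulation with chi-square tests, 100 per arm and the same response rate in both doses gives:

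| Rates | 2g alone | Global and 2g | All three steps |
|---|---|---|---|
| 21.6% v 11.8% | 47% | 37% | 28% |
| 25% v 10% | 82% | 76% | 69% |

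**Do the oral data rule out 15 points?** The Phase 2a difference is 11/51 − 6/51 = 0.098, with standard error √[(0.2157×0.7843 + 0.1176×0.8824)/51] = 0.0732. The Wald 95% interval is 0.098 ± 1.96×0.0732, or −4.5 to 24.1 points. They do not.

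**The case against.** The strongest reply is that this is rationale text with little effect. A sponsor may plan for a target larger than the effect seen in a small earlier study, and the Phase 2a interval includes 15 points. No endpoint, analysis set, model or test uses SAP 2.2.9. A reader might infer that the SAP presents 300 as sufficient. The documents do not support that: the SAP's protocol summary calls 300 a minimum, and SAP 2.2.10 says that the number may be increased at the interim to reach at least 80% power. All of this stands, and it limits the consequence.

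It does not remove the contradiction. SAP 2.2.9 does not offer 15 points as a target for the oral product. It derives the figure from extrapolated data and attributes it to a topical study.

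Two further readings are tempting and go too far:
- That SAP 2.2.9 claims 80% power. It states none. The 80% is a back-calculation: it is the power that returns 100 per arm for 10% against 25%.
- That the text was taken from the cream programme. The word topical, the 4-week data and the 28-day cream study all point that way, but SAP 2.2.9 names only the Phase IIa results. The source remains an inference, and the contradiction does not depend on it.

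**Conclusion.** The concern holds in this form: SAP 2.2.9 describes the wrong formulation, extrapolates although Week 8 data exist for the oral product, and conflicts with protocol 12.3 on the planning effect, 15 points against 9.8. For a single comparison at 100 per arm and two-sided 5%, that is 80.2% against 45.9% power, or 100 against 227 patients per arm for 80%.

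A reader might conclude that one calculation is wrong. Neither is; each follows from its own inputs. The fault is in the assumed effect and where it comes from, and its consequence is confined to the stated justification.

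The sizes rest on the normal approximation with no allowance for dropout. The sequence figures also assume equal response in both doses, although the oral Phase 2a study tested only 2g, and they use chi-square tests in place of the planned repeated-measures model.

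**What to change.** In SAP 2.2.9, delete the topical wording and the extrapolation from Weeks 2 to 4. Then choose one:

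- **(a) Use the protocol's basis.** State that, with the oral Phase 2a Week 8 rates of 21.6% (2g) and 11.8% (placebo), 100 per arm gives about 45% power at two-sided 5% for a single dose-placebo comparison.
- **(b) Keep 15 points as the target.** Justify it for the oral product, state about 80% power at two-sided 5% for a single comparison, and give the 45% at 21.6% against 11.8% beside it.

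Under either option, add that power is lower under the SAP 2.2.8 sequence. Assuming equal rates in both doses and chi-square tests, it is about 37% for global plus 2g and 28% for all three steps at 21.6% against 11.8%. At 25% against 10% it is about 76% and 69%.

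The cost is SAP wording only. The stated power becomes less favourable. Enrolment and analyses do not change.
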